
2. *Stakeholder Enhancements (Partnership) Intervention*. The Partnership intervention will involve all of the above components of the Wellness intervention, and the two additional components identified by patients and stakeholders from the recent PCORI award and from relevant research literature. The Wellness intervention will focus on these two evidence-based enhancements working together in a school-wide strategy focused on clinicians working actively on school teams and assisting in promotion/prevention -Tier 1, early intervention - Tier 2, and treatment -Tier 3 within the multi-tiered system of support (MTSS). Clinicians will actively participate in the MTSS to help improve school culture, and enable effective implementation of all intervention elements including SEs. In each of the 11 Partnership schools, a parent leader, and school-employed mental health professional (e.g., school psychologist, counselor) will be assigned to work with the clinician and implementation team, one day per week through resources allocated from the grant. The two SEs will be: Mental Health Literacy and Stigma Reduction. To enhance mental health literacy and focus purposefully on reducing the stigma of seeking SBH services, a program called The Guide, developed in Canada and beginning to be used in the US and other nations, will be used (see [www.teenmentalhealth.org/curriculum](http://www.teenmentalhealth.org/curriculum)). The Guide is a teacher-delivered mental health curriculum for middle and high schools. Teachers, as supported by clinicians and parent leaders will deliver the program, which includes didactics, interactive classroom activities, and experiential learning. The Guide consists of modules focused on stigma and reducing it, understanding mental health, mental health challenges, and seeking help/finding support, with positive outcomes of increased mental health knowledge and reduced stigma for participating students (43,44). The program is being used throughout Canada, in Washington State, and in a number of other countries, and it has strong feasibility and acceptability data, helping to support its growth and sustainability in

PRINCIPAL INVESTIGATOR: [name]

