### **Study Design.**

*Measures and Measurement Plan.* All measures chosen for use in the study are in the public domain and have strong psychometric properties (e.g., internal consistency, test-retest reliability, concurrent validity). There will be two streams of data collection involving students. The first will be data collected to reflect school-wide impacts of the Partnership Condition focusing on academic record variables of students' grades, attendance, lateness and discipline referrals (including office discipline referrals and suspensions), and school climate. School-wide academic record data will be collected for all students and de-identified to the research team (it is considerably less burdensome for schools to share deidentified data for all students than to share for a sample of them). School climate data will be collected for a sample of about 60 students (3 randomly selected classrooms), and 25-40 staff (requesting all staff complete) at each of the 22 schools. School-wide academic record data will be collected once annually for the academic year prior to study start (2018-19), and will be collected each year for the three years of intervention vs. comparison, per procedures that we are replicating based on the current NIJ-funded RCT. Selected students and staff will complete the School Climate Survey (SCS) a free, online school climate survey from the US Department of Education (<https://safesupportivelearning.ed.gov/edscls>). The SCS is available as a web-based platform and includes a suite of school climate surveys for students, instructional staff, and non-instructional staff. Staff and students will be asked to

PRINCIPAL INVESTIGATOR: [name]

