complete the survey, which assesses the dimensions of engagement, safety, and environment once annually at the end of each academic year for the four years of intervention vs. comparison (2019-20, 2020-21, 2021-22, 2022-23). Due to the COVID-19 pandemic, the team was unable to collect SCS data from students in [REDACTED] schools during the first academic year (2019-2020). While this means a compromised set of Year 1 data on school climate for the [REDACTED] site, such measurement is intact for SC, and we will still be able to document trends in time in school climate in [REDACTED] for years 2-4 of the intervention vs. comparison period. Additionally, the study team will collect rosters of classrooms receiving The Guide Curriculum (GC). This will enable two sets of analyses: first, we will document which students receiving Tier 3 services and participating fully in the study are exposed to GC and account for this in terms of interventions received in analyses. Second, this will significantly expand a second level of enrollment for the study, as we will have de-identified academic records for all students (related to recently approved amendments), and will explore impacts of the GC on academic record variables (e.g., discipline problems, grades, attendance) for students in classrooms in Partnership schools receiving it compared to students in demographically comparable classrooms from Wellness schools that do not receive it.

The second stream of data collection will focus on students receiving Tier 3 services and consenting to be in the study. Clinicians will collect these measures with students and families at intake, every three months, and at case closure, using an electronic data portal coordinated by [name] and the Informatics Team at the Medical University of South Carolina (MUSC). The measurement strategy for each of the study aims is presented here:

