In addition to primary intent to treat analyses, we plan to use quasi-experimental methods to test dose-response, and treatment engagement on a core aspect of the Partnership Condition – the mental health literacy intervention through the program, The Guide. In Partnership schools, this intervention has continued to be implemented through all phases of the pandemic, going from virtual in some phases to in-person in classrooms. We are able to access student academic records (demographics, grades, attendance, discipline) for students in Partnership classrooms receiving The Guide, as well as students in comparable wellness classrooms not receiving it. Per below, we have a large sample size to pursue these supplementary analyses. In these analyses, we will be overpowered (MDES below .1) to understand the impact of this mental health literacy intervention on student functioning, including examining dose of intervention given variability in teachers' delivery of it. We also have broader school climate data to explore the impact of the Partnership intervention on this variable (collected fall, 2019; fall, 2020; fall, 2021; spring, 2022; and spring, 2023).

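### The supplementary Guide analysis compares Partnership classrooms with Wellness classrooms, so it estimates The Guide plus the rest of the Partnership package and should not be read as the effect of the curriculum

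*Combined protocol and SAP*

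**What the plan says.** The Measures and Measurement Plan says the team "will explore impacts of the GC on academic record variables" (GC is The Guide curriculum), and defines the comparison as one "for students in classrooms in Partnership schools receiving it compared to students in demographically comparable classrooms from Wellness schools that do not receive it".

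The Analytic Plan returns to this analysis. It is additional to the primary intention-to-treat analyses: "we plan to use quasi-experimental methods to test dose-response, and treatment engagement". The data named are records of students in Partnership classrooms that receive The Guide, "as well as students in comparable wellness classrooms not receiving it". The intended reading is explicit: "In these analyses, we will be overpowered (MDES below .1) to understand the impact of this mental health literacy intervention on student functioning". Dose is to be examined through differences in teachers' delivery, but no dose model is given.

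The Guide is one part of the Partnership arm. Each Partnership school is also assigned a parent leader, and a "school-employed mental health professional (e.g., school psychologist, counselor) will be assigned to work with the clinician and implementation team", one day per week (Stakeholder Enhancements (Partnership) Intervention). The same section adds PCOMS, parents on MTSS teams, and cultural-responsiveness and bias training. During the intervention years ECHO clinics run for Partnership schools only (Engagement in Quality Improvement and Dissemination).

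On data, "School-wide academic record data will be collected for all students and de-identified to the research team", and rosters of Guide classrooms with school-issued student numbers are to be obtained.

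**The concern.** The question concerns one component, but the comparison is between arms. A student in a Guide classroom differs from a matched Wellness student in receiving The Guide and also in attending a school with every other Partnership component. Neither document section limits the conclusion to the package, and neither names Partnership students without The Guide as a comparator.

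This is separate from the question of which teachers choose to deliver the curriculum. Perfectly matched classrooms would leave it in place.

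What is at stake is attribution. This is the plan's one explicit contrast for crediting a single component with changes in grades, attendance and discipline, and the plan describes it as having ample power. A district weighing a curriculum against added staff time or family partnership would want to know which of them produced any difference, and this contrast cannot say.

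**Working it through.** **Inputs.** 22 schools, 11 per arm (Analytic Plan). 80% power, 30% of variance explained, MDES .29 at N = 1225 and .28 at N = 1400 (Power considerations). MDES below .1 for the Guide analyses (Analytic Plan). About 12,000 students in Year 1 and 20,000 overall (Recruitment Plan); 20,000 serves as an upper bound because the N of the Guide analysis is not stated. Alpha and ICC are not stated either; I assume two-sided .05 and vary the ICC.

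**The plan's own figure.** With J schools and n = N/J students per school,

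MDES = M × √[ICC(1−R²)/(0.25J) + (1−ICC)(1−R²)/(0.25Jn)], where M = t(.975, 20) + t(.80, 20) ≈ 2.945.

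For the main trial at N = 1225, an ICC of .059 with R² = .30 at both levels gives 2.945 × √(.059×.70/5.5 + .941×.70/306.25) = 2.945 × √(.00751 + .00215) = .29, as stated. If R² applies at one level only, the implied ICC is .041 (student level) or .052 (school level). ICC .059 at N = 1400 gives .286 against the stated .28.

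For the Guide analysis the same formula gives:

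| ICC | N = 5,000 | N = 12,000 | N = 20,000 | unlimited N |
|---|---|---|---|---|
| clustering ignored | .066 | .043 | .033 | – |
| .01 | .126 | .114 | .111 | .105 |
| .059 | .265 | .260 | .258 | .256 |

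Below .1 requires an ICC of about .007 or less at N = 12,000, or .008 or less at N = 20,000. The claim can be neither confirmed nor refuted, since N and ICC are missing and the ICC for academic records may differ from the one back-calculated here. The point below does not depend on it: MDES describes precision, not what is being estimated.

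**What the contrast estimates.** Write μ(P,G) for Partnership students with The Guide, μ(P,0) for Partnership students without it, and μ(W,0) for Wellness students. Then

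μ(P,G) − μ(W,0) = [μ(P,G) − μ(P,0)] + [μ(P,0) − μ(W,0)] = g + r,

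where g is the effect of adding The Guide in a Partnership school and r is the effect of the rest of the package. Illustrative values, not from the documents:

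| g | r | planned contrast | within-Partnership contrast |
|---|---|---|---|
| 0 | .05 | .05 | 0 |
| 0 | .10 | .10 | 0 |
| 0 | .20 | .20 | 0 |
| .10 | .10 | .20 | .10 |

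**Does anything planned remove r?**

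- Demographic matching does not, because r is fixed by arm.
- A larger N does not; it gives a more precise estimate of g + r.
- The BART models condition on baseline covariates. No Wellness classroom has The Guide and no Guide classroom lacks the rest, so there is nothing to condition on.
- The dose analysis might. Non-zero dose exists only in Partnership schools, so a dose slope estimated within them drops the school-wide part of r. Pooling Wellness as dose zero would bring r back in. The plan does not say which is intended.

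**Is there a within-Partnership comparison group?** Direct training covers three teacher leaders per school, one per grade, and other teachers are encouraged to take an online course. In spring 2020 the plan names two schools that kept live delivery going. Non-Guide Partnership students therefore very plausibly exist, but their number is not documented.

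**Effect of diffusion.** If non-Guide Partnership students receive a share s of The Guide's effect, the within-Partnership contrast becomes (1−s)g, and non-Guide Partnership versus Wellness becomes r + sg. The two still add to g + r, so reporting all three contrasts shows where the difference arises.

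**The case against.** The strongest reply is that this is an exploratory analysis, labelled supplementary and quasi-experimental, of what the plan calls a core part of the Partnership condition. No aim or primary outcome rests on it. That stands, and it limits the consequence. A reader might infer that the trial's main comparison is compromised; it is not, because the primary analyses compare the arms as randomised.

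A second reply is that The Guide and the rest of the package are not cleanly separable. Parent leaders support teachers in delivering The Guide, a Guide consultant serves as content expert on ECHO calls, and the two enhancements are meant to work together. PCOMS operates in therapy sessions, while the plan expects about 20% of students to have mental health needs, so its average effect on whole-classroom records is diluted. This also stands: r may be modest and its boundary with g is blurred. It does not make the contrast an estimate of The Guide.

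A reader might also size the bias by taking .29 as the package effect and assigning a share to the other components. The documents do not support this. The .29 is a minimum detectable effect for enrolled students, not an expected effect, and it does not refer to school-wide records.

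Finally, a reader might conclude that the within-school contrast should replace the planned one. It is not randomised. It exchanges confounding by arm for selection of teachers, and the plan deliberately spreads The Guide to other teachers through grade-level and MTSS meetings. It is complementary evidence, not a replacement.

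**Conclusion.** The concern holds as a mismatch between comparator and interpretation. The planned contrast estimates g + r, and the plan reads it as g. This follows from receipt of The Guide being nested in the Partnership arm, and needs no numerical assumption. The size of r on school-wide records is not given in the documents and may be small; the values .05 to .20 above are illustrations only. The primary intention-to-treat results do not change. What changes is the conclusion allowed: the analysis as planned can support a statement about Partnership schools in classrooms that received The Guide, not about the curriculum. Feasibility of the added comparison rests on there being enough non-Guide Partnership students, which is plausible but undocumented.

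**What to change.** In the Measures and Measurement Plan and the Analytic Plan:

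1. Label the existing contrast *Partnership including The Guide versus Wellness*, and state that it is not interpreted as the effect of The Guide.
2. Add, as complementary non-randomised evidence, a within-Partnership comparison of students on a Guide roster (or by delivered dose) with students in the same school, grade and year who are not on one. Use school or school-by-year effects and adjust for prior records where available. Estimate dose-response within Partnership schools, without pooling Wellness as dose zero.
3. Report non-Guide Partnership students versus Wellness students alongside.

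The cost is SAP wording and some modelling. All-student records and Guide rosters are already planned, and the plan already foresees adding Guide participation to analyses of student records.

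Limits to state with the results:

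- Teachers who deliver The Guide are selected.
- Diffusion to other classes pulls the within-school estimate toward zero.
- Cells in which a whole grade received The Guide drop out.
- Rosters are planned only for Guide classrooms, so no class identifiers are documented for non-Guide students and a classroom term for them may not be possible.
- No prior-year records are documented for sixth graders.

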
Enhancing Family-School-Mental Health Partnerships. The Partners for Change Outcome Management System (PCOMS) has been used for more than two decades to enhance patient involvement in mental health services and to improve the therapeutic alliance between patients and clinicians (see 45-47). Foundational to the program are two brief measures: The Outcome Rating Scale (ORS, 46) and the Session Rating Scale 3.0 (SRS, 47). The ORS measures progress in EB symptoms and social relationships (completed at the beginning of the session) and the SRS measures therapeutic alliance including quality of the relational bond, and agreement on treatment goals and methods (completed at the end of the session). Both scales take less than a minute to complete and score and are available for free online at [www.talkingcure.com](http://www.talkingcure.com). The PCOMS program helps to promote dialogue on how therapy is proceeding, increases chances for active student/parent input, and helps to assure that both groups are in sync with treatment plans and progress. In addition to the PCOMS system, SBH efforts in Partnership schools will be enhanced by active participation of the parents on MTSS teams, which will also receive regular guidance, ideas and resources from the study's SAB (see Engagement Plan). Please note that family-school-mental health partnerships will also be enhanced by ongoing involvement and guidance by the family advocate at each site, and parent leader at each of the 11 Partnership schools.

PRINCIPAL INVESTIGATOR: [name]

In addition, in each of the 11 Partnership schools, clinicians and MTSS teams will conduct trainings on both Partnership Group enhancements, as appropriate. Clinicians and MTSS teams should leverage grade-level meetings to provide trainings and information as appropriate for each school environment.

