*Aim 1: Evaluate the impact of the Partnership enhancements in increasing the number of students and families receiving services and expressing satisfaction with them.* For this primary aim, and per experiences from prior RCTs (18,19), as mentioned, we will collect data for each student on the number of sessions conducted by the SBH clinician in categories of assessment; individual, group and family therapy; case management; and teacher consultation. In addition, during the COVID-19 school closure period we will document which students receive any of these services through telehealth, and will document this form of service received. This will enable coding of overall productivity, for types of services, and for family involvement in care. To measure satisfaction with services, at the three month or case closure assessment points, we will collect the Client Satisfaction Questionnaire-8 (CSQ-8) from students and parents. The CSQ-8 is a brief, widely used 8-item measure for use with youth aged 11 and older and adults (50).

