Help Seeking (HS; 15 items), and Perceived Stigma (PS; 12 items). The MHK and PS subscales of the GCA have strong psychometric properties and will be used in the study. The MHK subscale includes 7 items on basic understanding of the brain, 9 items on common mental disorders, 7 items on stress and good mental health, and 5 items on causes of mental disorders and treatment. The PS subscale includes 5 items reflecting personal stigma (personal attitudes toward people contending with mental health problems) and 7 items reflecting social distance (the degree to which people are willing to accept people with mental health problems into regular social life). To further assess the reduction in Perceived Stigma, we will also collect the PS subscale from the GCA from parents of students receiving Tier 3 services within Stream 2 data collection using the teacher/parent version of the measure.

The enhancement focused on Family-School-Community Partnerships will be measured in three ways. First, the 24 SBH clinicians will complete the 63-item SBH Quality Assessment Tool (SBHQAT; 29) in August and May in each of the four intervention versus comparison years (2019-20, 2020-21, 2021-22, 2022-23). Second, clinicians and students receiving Tier 3 services will complete the Therapeutic Alliance Scale for Children-revised (TASC; 55), a measure of therapeutic alliance across treatment. Third, as mentioned, family participation and engagement in their children's mental health treatment will be measured using the Parent Participation Engagement Measure (PPEM; 48), which assesses parent participation behaviors with the therapist as reported by both youth and their parents/guardians.

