The second avenue of recruitment will be for students receiving Tier 3 treatment services. These students/parents will be consented using electronic consent (e-consent) in REDCap, with the consent form appended at the beginning of the survey. Participants and their parents will be required to go through the informed consent process and digitally sign the consent form using a mobile tablet device before proceeding into the survey questionnaire. MUSC has successfully piloted e-consent in REDCap with other IRB approved research studies. Given challenges with parents' ability to attend meetings at the school to complete the enrollment process, the study team developed protocol to allow for consent to be gained via phone and intake to be completed remotely via phone or computer. This flexibility allows enrollment to continue, and not be hampered by potential transportation or financial constraints that may otherwise prevent low-income families from participating. Additionally, as result of the COVID-19 crisis, procedures were developed to allow students to assent into the study via telephone or video conference. Students and parents may provide assent/consent via phone, after viewing consent materials and having the opportunity to ask questions of the clinician. Intake assessments can be completed verbally (via phone or video conference) or a link to complete surveys online may be sent via email or directly through the REDCap program by the clinician or research manager.

PRINCIPAL INVESTIGATOR: [name]

Based on current prevalence data, twenty percent (2,14) of students are expected to present with mental health challenges (n= 4,000). Of these students, based on the experience in similar studies the research team estimates that 30% will consent to participate representing the recruitment goal of 1,225 students by the end of the 2022-23 academic year. The rate of recruitment will be higher initially due to enrollment of students currently receiving services, however, over the course of the study an average of 35 students per month (during the academic year only, or four years times 9 months for 36 months total) will be enrolled. Note: significant changes to enrollment targets have been made during this project largely related to the unanticipated and unprecedented impact of the COVID-19 pandemic which temporarily closed school buildings and changed mental health care services starting in March 2020.

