There are essentially six classes of student participants, with groups based on grade level at the start of the intervention vs. comparison (IvC) period of the study, which begins in the 2019-20 school year. There is a four-year IvC period, 2019-20, 2020-21, 2021-22, and 2022-23. Group A will be in the 6th grade in 2019-20, with students experiencing 1-3 years of services in this time interval. These students could have received services in 6th, 7th and/or 8th grades during the IvC period. Group B will be in the 7th grade in 2019-20, with students experiencing 1-2 years of services in this time interval. These students could have received services in 7th and/or 8th grades during the IvC period. Group C will be in the 8th grade in 2019-20, with students experiencing 1 year of services in this time interval. Group D will enter the study in 6th grade in 2020-21. Group E will enter the study in 6th grade in 2021-22. Group F will enter the study in 2022-2023 while in 6th grade.

*Identifying eligible participants.* Participants already receiving treatment and those newly referred for services will be eligible to participate and recruited by their SBH clinician. Throughout the implementation phase (years 1-4) each school will use their existing referral process to identify students in need of treatment which will be followed up and confirmed by the SBH clinician prior to enrolling them in the study.

*Overcoming barriers to enrollment.* In addition to our successful experiences with the opt-out procedure to be used for stream 1 data collection, both mental health centers have participated in extensive and similar research with the investigators leading this study. The SAB will provide input on the development of consent materials, and methods of communication, making sure that they are appealing. The process of utilizing e-consent will be convenient and streamlined for Tier 3 participants. Additionally, participant incentives are proposed, in the amount of \$20 per parent assessment battery, and a token of appreciation for each student assessment battery to incentivize participation.

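### The satisfaction measure for primary Aim 1 is collected by the student's own clinician, with no stated barrier to that clinician seeing the answers, and only Partnership clinicians also elicit and discuss alliance ratings

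*Combined protocol and SAP*

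**What the plan says.** All references are to the combined protocol and SAP.

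- **Who collects.** The Measures and Measurement Plan, second stream, says: "Clinicians will collect these measures with students and families at intake, every three months, and at case closure", through an electronic portal. Under Identifying eligible participants, students are "recruited by their SBH clinician", so the collector is the treating clinician.
- **What is collected for Aim 1.** The Aim 1 measures text calls this a primary aim and states: "at the three month or case closure assessment points, we will collect the Client Satisfaction Questionnaire-8 (CSQ-8) from students and parents". No intake CSQ-8 is planned.
- **Alliance.** Under Additional Measures, the TASC is completed by clinicians and by Tier 3 students in both arms. It serves a secondary aim.
- **What differs by arm.** PCOMS is described under Enhancing Family-School-Mental Health Partnerships, the second Partnership addition. It is not among the four Wellness components. Of its two brief scales, the "SRS measures therapeutic alliance including quality of the relational bond, and agreement on treatment goals and methods (completed at the end of the session"). Promoting discussion of how therapy is going is a stated purpose of the programme.
- **Knowledge of arm.** Under Comparators, supervision, training and meetings are separate by condition. No blinding is described.
- **Alternative routes.** Under Recruitment Plan, intake assessments may be done verbally, or "a link to complete surveys online may be sent via email or directly through the REDCap program by the clinician or research manager". This is written for intake only.

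**The concern.** The CSQ-8 asks families to judge the service they received, and the person who provided that service gathers the answers. Some courtesy towards one's clinician is expected in both arms and would largely cancel in the comparison. The difficulty is that the setting for the answers is not the same in both arms. A Partnership student will usually have rated the working relationship for this clinician, and talked those ratings over, before the CSQ-8 and TASC fall due. A Wellness student will not.

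Randomising schools does not protect against this, because the difference arises after randomisation and is part of one arm. A larger sample does not remove it. The analysis cannot adjust for it either: without an intake CSQ-8, the difference-score approach in the Analytic Plan is unavailable and individual response style cannot be taken out. At stake is whether an arm difference in CSQ-8 can be read as a difference in satisfaction.

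**Working it through.** **Step 1. Is there a safeguard elsewhere?** Three places could supply one.

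- Data Management describes user rights and data access groups in REDCap, but does not say that treating clinicians are barred from the CSQ-8 or TASC.
- Protections Against Risk promises confidentiality in general terms and does not mention the clinician.
- The link under Recruitment Plan concerns intake, when the CSQ-8 is not collected.

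One sentence in the Partnership section says the Wellness intervention will focus on the two enhancements. It reads as a slip, since the same section presents them as additions to Wellness, but it should be reconciled because it blurs which arm receives PCOMS.

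**Step 2. The plan's own precision.** Inputs from Power considerations: 22 schools, N = 1225, 30% of variance explained by pre-test covariates, 80% power, MDES .29. Assumed because not stated: two-sided 5% test and 20 df. The ICC is also not given, so .29 cannot be reproduced directly; I solved for the ICC instead.

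MDES = M × √[ICC(1−R²)/(0.25J) + (1−ICC)(1−R²)/(0.25·J·n)]

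- M = 2.086 + 0.860 = 2.946
- J = 22, so 0.25J = 5.5; n = 1225/22 = 55.7; R² = .30 at both levels
- ICC = .0592 gives √(.00753 + .00215) = .0984, and 2.946 × .0984 = .290

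The stated figure is therefore attainable with an ICC near .059 (.041 to .067 across other placements of R², degrees of freedom, and t or normal multipliers).

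**Step 3. Standard error for the CSQ-8 contrast.**

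- As planned: .29/2.946 = .0984 SD.
- Without the covariate gain, since the CSQ-8 has no pre-test: .0984/√.70 = .1177 SD.

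**Step 4. Chance of a significant result from a reporting shift alone.** The shift *b* is an assumption; the documents give none. With no true effect, the noncentrality is b/SE on 20 df, two-sided 5%.

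| Assumed shift (SD) | b/.0984 | Rejection rate | b/.1177 | Rejection rate |
|---|---|---|---|---|
| .10 | 1.02 | 16% | 0.85 | 13% |
| .15 | 1.52 | 31% | 1.27 | 23% |
| .20 | 2.03 | 49% | 1.70 | 37% |

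The nominal rate is 5%. Using 19 df gives the same rounded percentages. If fewer than 1225 students supply a CSQ-8, the standard error grows and the rates fall. The fall would be modest, because the school term (.00753) outweighs the student term (.00215).

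**The case against.** The strongest reply is that the collection procedure is the same in both arms: same kind of collector, same schedule, same portal. The arm-dependent part rests on a supposed effect of practice with session ratings, and nothing in the plan says that practice raises scores. PCOMS is meant to invite input, so it could make Partnership students franker and lower their scores. It is also meant to improve alliance, which the Conceptual Framework names as a mechanism, so a higher score may be real. All of this stands, and it is why no direction or size can be claimed.

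A reader might infer that clinicians read the items aloud, enter the answers or look at them. The documents do not say so. Consent is signed on a tablet before going on to the questionnaire, which suggests self-completion, and an implementation manual that is not among the documents may cover the procedure. The gap is an unspecified procedure.

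A reader might also infer that Partnership satisfaction will be inflated, or that Aim 1 as a whole is compromised. Neither is supported. Session counts, the other part of Aim 1, are a separate outcome. The TASC is secondary. The PPEM mainly describes the parent's own participation and is not a rating of the clinician, so it is left out here.

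Two practical objections also stand. Private completion cannot undo practice with PCOMS ratings. And with the study period ending in June 2023, most forms may already exist.

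**Conclusion.** The concern holds as a risk to interpretation. The treating clinician, whose knowledge of the arm is inferred from separate training and supervision, collects the CSQ-8 and the student TASC. No stated rule keeps the answers from that clinician, and only Partnership adds the eliciting and discussion of alliance ratings. The satisfaction contrast is therefore open to reporting differences by arm, and the plan cannot separate these from a real PCOMS effect.

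The size is unknown. The 16% to 49% range, or 13% to 37% without the covariate gain, depends on an assumed .10 to .20 SD shift, no true effect, and the precision implied by the stated MDES. A shift the other way would produce errors at the same rates in favour of Wellness, or hide a real gain. This is a worthwhile, inexpensive improvement and a limitation to report. It does not invalidate the trial.

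**What to change.** For the CSQ-8 and student TASC at three months and case closure, in both arms:

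1. Have the student or parent self-complete on the study tablet or by a REDCap link sent by the research manager.
2. Set REDCap rights so that the treating clinician cannot view these answers, and tell respondents so on the first screen.
3. Record the mode of completion. For forms already collected, report mode by arm where records allow; REDCap's audit trail may help.
4. Treat any analysis that leaves out clinician-administered forms as a descriptive sensitivity analysis only. Mode is determined after randomisation and may differ by arm, so excluding on it can itself introduce bias.
5. State as a limitation that these steps remove the clinician's presence and sight of the answers, but not any effect of PCOMS practice on how students rate.

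The cost is a rights setting and a procedure amendment, with tools the study already has. Completion may fall slightly where families relied on the clinician's help. The procedural steps reach few of the data collected by June 2023; for those, items 3 to 5 are what remains.
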